### **Human Subjects Protection**

## **Risk to participants**

The Diabetes Prevention Program (DPP) study, a placebo-controlled study of metformin vs. lifestyle intervention in persons with pre-diabetes (included subjects with fasting blood glucose 90-125 mg/dL, n = 3,234) provides insight into side effects of long-term metformin administration in the elderly and non-diabetics. Of note, the most common side effect was not hypoglycemia, but gastrointestinal symptoms (see table below).

**TABLE 3. ADVERSE EVENTS.**

EVENT	PLACEBO	METFORMIN	LIFESTYLE
Gastrointestinal symptoms (no. of events/100 person-yr)*	30.7	77.8†	12.9†
Musculoskeletal symptoms (no. of events/100 person-yr)‡	21.1	20.0	24.1†
Hospitalization			
One or more admissions (% of participants)	16.1	15.9	15.6
Rate (no. of admissions/100 person-yr)	7.9	8.4	8.0
Median stay (days)	3	3	3
Deaths (no./100 person-yr)	0.16	0.20	0.10

\*Gastrointestinal symptoms included diarrhea, flatulence, nausea, and vomiting.

†P<0.0167 for the comparison with placebo.

‡Most participants with musculoskeletal symptoms had myalgia, arthritis, or arthralgia.

As far as common side effects, GI side effect and diarrhea are transient and usually pass after a week of therapy. In the DPP study, 3-5% of subjects had continuous diarrhea; this portion of subjects would be excluded in the present trial during the run-in, dose-titration period. No one had metformin associated lactic acidosis. Hypoglycemic events were either not in evidence or reported.

Weight loss is a common occurrence with metformin and will be monitored. In such a case some patients may complain of hypoglycemic symptoms (rapid heartbeat, feeling light-headed or fainting, and nausea), and in this case subjects will be asked to refrain from taking their next dose. Subjects may not need medical interventions, but will be given instruction for fruit juice or other carbohydrate and to call the coordinator immediately to come in for a blood glucose check. Levels will be checked by finger (Accucheck) and labs to LabCorp to confirm levels. If blood glucose levels are < 60 mg/dL they will be removed from the study and replaced by an additional participant. No more side effects were noted in the elderly; in fact, they had a better adherence to therapy. Young and elderly had the same rates of GI side effects and diarrhea.

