**Exclusion Criteria**

eGFR <45  
Type 2 diabetes (HbA1c>6.5) or type 1 diabetes  
Any tobacco or nicotine product use in the past year  
Low vitamin B12 Levels (< 300 pg/mL)  
Self-reported severe difficulty or inability to walk 400m or climb 10 steps (from Q 2 and 19 on PAT-D)  
Self-reported difficulty or inability to perform basic ADL functions (from Q 10, 13, 14, 16 on PAT-D)  
Excessive alcohol use (>14 drinks/week)  
Cancer requiring treatment in past year (except skin)  
Dementia – diagnosed and/or MoCA score <18  
Parkinson's or other neurological disease  
Chronic liver disease or cirrhosis  
End stage renal disease or on dialysis  
Rheumatic conditions (Rheumatoid arthritis, lupus, and any other autoimmune disease the PI deems them to be ineligible for)  
Thyroid problems the PI deems them to be ineligible for  
Recent or recurrent exacerbation of gout  
Involved in another interventional study  
Hemoglobin  $\leq$ 8 or diagnosed with anemia  
Recent unintentional weight change (+/- 10 lbs. in the last 12 months)  
BMI <18.5  
Likely to not follow the protocol  
PI deems unfit to participate  
Already taking Metformin or any other drug intended to treat diabetes

***Screening, consent and randomization.*** Individuals who pass the telephone screening will be scheduled for a visit to the Geriatric Research Clinic (GRC) in the Sticht Center on Aging for a screening visit (SV). Before any data collection, all participants will provide written informed consent and complete a HIPAA authorization form in accordance with the Wake Forest School of Medicine Institutional Review Board policies. Individuals who meet all eligibility criteria and provide informed consent will be invited back for the first baseline visit (BV). At the end of BV, participants will be randomized to one of the two study intervention sequences (metformin followed by placebo or placebo followed by metformin) using a web-based randomization scheme (developed by [name]). The randomization sequences will be unknown to the research staff. Intervention assignment will be generated using a program that the study coordinator will access from his/her PC through the study website.

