#### **Schedule and organization of assessment visits**

All assessments will be conducted during 4 visits (before and after each intervention) according to the chart below. All examiners are trained in the standardized conduct of all assessments before data collection. Participants will be instructed to wear appropriate and comfortable clothing, and standardized written instructions will be provided prior to each study visit.

Assessment timeline	Visit code	SV	BV	On trial	Mid	On trial	FV
Activity/assessment	Week number	-4	0		12-14		24-26
Informed consent, review inclusion/exclusion criteria, demographics, weight, height, BP and pulse, fasting screening blood draw (metabolic blood panel, lipid panel, CBC, Vit B12, Hba1c), eSPPB, cognitive screen (MoCA), waist circumference, medical history, medications PAT-D,		X					
Blood collection for methylomic and transcriptomic, bioenergetic capacity, CBC, and blood for storage, DSST, leg press, grip, MATsf, and 6MWD			X				
Randomization			X				
Crossover – Dispense New Medication					X		
Vitals, blood collection for methylomic and transcriptomic, bioenergetic capacity, and blood for storage, CBC, CMP, lipids, Hba1c, eSPPB, MoCA, DSST, leg press, grip, PAT-D, MAT-sf, 6MWD					X		X
Health Maintenance							X

The screening visit (SV) will be conducted in the morning following an 8-hour fast for measurement of lipids, blood count, Hba1c, Vitamin B12, and a metabolic panel for screening purposes. Vitals (blood pressure, pulse, height, weight, and waist circumference) are collected and the blood draw completed, participants will be given a snack and continue with the remainder of the visit. First, the expanded short physical performance battery (eSPPB) will be administered and scored and then undergo a cognitive screen, assessed using the Montreal Cognitive Assessment (MoCA), and a medical history, review of medications and dietary supplements. We will also ask about the participants demographics and physical abilities using the Pepper Assessment Tool for Disability (PAT-D),

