The first baseline visit (BV), will be conducted in the morning following an 8-hour fast for blood collection for methylomic and transcriptomic measures, bioenergetic capacity, CBC, as well as blood for storage. After these measures are complete, participants will be given a snack and will continue with the rest of the visit consisting of lower extremity muscle power (Nottingham Power Rig), grip strength, 6 minute walk distance test (6MWD), and the Mobility Assessment Tool – short form (MAT-sf). Cognitive function will be assessed using the Digit Symbol Test (DSST). Once the visit is complete, the participant will be randomized and placed in one of the following groups discussed below. Participants will be provided with an information sheet that will provide additional details on how and when to take the medication, who to call if they have any problems, possible side effects, and what to do should they encounter any side effects.

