#### Interventions and Interactions

Eligible participants will receive both interventions (3-month metformin treatment and 3-month placebo). Randomization will be used to determine the order in which the participants receive each intervention (i.e., 15 participants with metformin treatment followed by placebo, and 15 with placebo followed by metformin treatment). Neither the participants nor the investigators know the intervention order of a participant. Metformin reaches peak plasma concentration within one to eight hours, has an average elimination half-life of 6.2 hours in plasma, and is cleared but not metabolized from the body by tubular secretion. Treatment with metformin and placebo will be initiated at a dose of 425 mg taken orally once a day at night for 7 days. After the week, the participant will be called to assess tolerance and will be asked to increase dose to one pill at night at a dose of 850 mg for one week. At the end of the second week, participants will be called again and if they tolerated the second dose, they will be asked to take two 850mg pills, one in the morning and one at night, for a total dose of 1700 mg which is within the range of the usual effective dose of 1500 to 2000 mg/day for the remainder of the 3 months. This dosing regimen was created in order to avoid or reduce possible gastrointestinal side effects. This can be modified if the

participant is experiencing any side effects and will be handled on a case by case basis. Each study visit where stored blood is obtained (BV, Mid, FV) may be rescheduled if the subject has a fever, infection, or has taken antibiotics within 24hrs of this scheduled visit.

All baseline assessments will be completed again at 12 weeks and again at 24 weeks as listed in the assessment table.

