**Cognitive function** will be assessed during screening using the Montreal Cognitive Assessment (MoCA) (26), participants must score  $\geq 18$  to be eligible. We will also assess psychomotor speed, attention, and working memory using the Digit Symbol Substitution Test (DSST) (27; 28). Participants are given a series of numbered symbols and then asked to draw the appropriate symbols below a list of random numbers. The score is the number of correctly made matches in 2 minutes (120 seconds).

**Body composition** will be measured by circumference measurements of the waist which is made with a tape measure.

**Blood lipids** (total cholesterol, HDL-Cholesterol, Triglycerides and calculated LDL levels) will be measured at a clinical lab and all results will be entered into the data system.

**Activities of daily living** will be assessed using the Mobility Assessment Tool – Short Form (MAT-sf). This is a novel, computerized tool for self-assessment of functional performance designed to reduce bias from factors such as age, gender and body image. The Pepper Assessment Tool for Disability (PAT-D) will also be used to assess the participant's ability to complete an array of important day-to-day activities without difficulty and, for a subset of activities, without personal assistance.

**Medication adherence:** Although we will attempt to enhance adherence by monthly calls to participants, there may be inter-individual variability in adherence to the medication. At the end of each phase, participants will be asked to return any unused pills for a pill count to determine participant adherence. Our primary analyses will be an intent-to-treat analysis of the effects of the metformin intervention, but secondary analyses will include adherence as a covariate.

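### Two safety rules take participants out after randomisation, although there is no run-in and the primary analysis is called intent-to-treat (minor)

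*Combined protocol and SAP*

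**What the plan says.** Two sentences in Human Subjects Protection, Risk to participants (text after Table 3), take people out of the trial. On the 3-5% who had continuous diarrhea in the cited diabetes prevention trial, the protocol says "this portion of subjects would be excluded in the present trial during the run-in, dose-titration period". On participants with glucose below 60 mg/dL it says "they will be removed from the study and replaced by an additional participant". Replacement is stated only for low glucose.

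The timing comes from other sections:

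- Screening, consent and randomization: "At the end of BV, participants will be randomized to one of the two study intervention sequences". The description of the baseline visit agrees: "Once the visit is complete, the participant will be randomized and placed in one of the following groups discussed below".
- Interventions and Interactions: "Treatment with metformin and placebo will be initiated at a dose of 425 mg taken orally once a day at night for 7 days". The dose then rises to 850 mg and to 1700 mg a day. Dosing can be changed if the "participant is experiencing any side effects and will be handled on a case by case basis".
- Schedule and organization of assessment visits: "All assessments will be conducted during 4 visits (before and after each intervention) according to the chart below". The chart shows SV, BV with randomisation, Mid (weeks 12-14) and FV (weeks 24-26).

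Under Other Data, Medication adherence, the plan states: "Our primary analyses will be an intent-to-treat analysis of the effects of the metformin intervention". The Analytical Plan fits a crossover analysis of variance with participant within sequence as a factor. It defines no analysis population and does not say how a missing period, a withdrawal or a replacement is handled.

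**The concern.** A run-in comes before randomisation, so exclusions during it leave the randomised comparison intact. Here the only titration is of the assigned blinded treatment, so an exclusion during titration is a post-randomisation exclusion, and for diarrhea it is likely to be related to treatment. The glucose rule has the same timing and adds a substitute.

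No section separates stopping study drug from leaving the study. Someone removed during metformin titration has no metformin-period outcome, and that outcome cannot be recovered at analysis. Followed as written, the plan would report an estimate from people who could stay on treatment under an intent-to-treat label. What is at stake is mainly whom the estimate describes. That matters for a pilot whose purpose is estimation with 95% confidence intervals and whose data are meant to inform a full-scale programme.

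**Working it through.** The plan gives no power, effect-size or dropout figure on this point, so there is nothing to reproduce. The check is the order of events, followed by a rough sizing.

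**Order of events**

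| Step | Section | Time |
|---|---|---|
| Randomisation | Screening, consent and randomization; BV description | end of BV, week 0 |
| Titration, metformin or placebo | Interventions and Interactions | first two weeks on treatment, after randomisation |
| Diarrhea exclusion | Risk to participants | during titration |
| Glucose removal and replacement | Risk to participants | on treatment |
| Next outcome visit | Assessment schedule | weeks 12-14 (Mid), 24-26 (FV) |

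Neither removal rule can act before randomisation. A metformin-first participant removed in metformin titration leaves before Mid with no post-baseline outcome. A placebo-first participant removed in metformin titration leaves after Mid and before FV, with the placebo period only. If participant within sequence is a fixed factor (the Analytical Plan does not say), a participant with one period uses that observation to fit their own effect and adds nothing to the metformin estimate. With a random factor they add only between-participant information.

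**Number removed for diarrhea.** Inputs: p = 3-5% (text after Table 3, with no arm or time frame given; that it carries over to metformin titration here is an assumption); n = 35 (Design) or 15 + 15 = 30 (Interventions and Interactions). Expected number = n × p; P(at least 1) = 1 − (1 − p)^n; P(at least 2) is the binomial tail.

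| n | p | Expected | P(≥1) | P(≥2) |
|---|---|---|---|---|
| 30 | 3% | 0.90 | 0.60 | 0.23 |
| 30 | 5% | 1.50 | 0.79 | 0.45 |
| 35 | 3% | 1.05 | 0.66 | 0.28 |
| 35 | 5% | 1.75 | 0.83 | 0.53 |

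Scaling to placebo by the Table 3 gastrointestinal rates, 30.7/77.8 = 0.395, would add 0.03 × 0.395 × 30 = 0.36 to 0.05 × 0.395 × 35 = 0.69 people. This is rough, because Table 3 counts all gastrointestinal symptoms, not continuous diarrhea.

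**Effect on the estimate.** Let k be the effect in those removed divided by the effect in those kept. The as-randomised effect is then (1 − p(1 − k)) times the effect in those kept, and the overstatement is 1/(1 − p(1 − k)) − 1.

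| k | p = 3% | p = 5% |
|---|---|---|
| 2 | −2.9% | −4.8% |
| 1 | 0 | 0 |
| 0.5 | 1.5% | 2.6% |
| 0 | 3.1% | 5.3% |
| −1 | 6.4% | 11.1% |

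The value k = 0 is plausible for someone who stops near week 2 and is measured near week 12: 10 × 7 × 24 / 6.2 = 271 half-lives at the protocol's 6.2 hours. It is not a bound.

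For an assumed true effect of 2-3 standard errors, bias b = effect × p(1 − k), and coverage = Φ(1.96 − b) − Φ(−1.96 − b):

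- k = 0: b = 2 × 0.03 = 0.06 to 3 × 0.05 = 0.15 SE; coverage 94.96% to 94.74%.
- k = −1: b = 0.12 to 0.30 SE; coverage 94.84% to 93.96%.

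**Precision.** With interval width proportional to t(n − 2)/√n, losing one or two pairs widens the interval by 1.9% or 3.9% from 30, and by 1.6% or 3.2% from 35.

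**Low glucose.** No rate is given, so this part is not quantified. The same section reports no evident hypoglycemia in the cited trial, so the number is probably small.

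**The case against.** The best case on the other side is that this changes no decision. By the working above, the shift is a fraction of a standard error and coverage stays at about 94-95%, in a pilot that says it lacks the power to test all its aims definitively. The part that can be sized rests on the softer sentence: the diarrhea remark sits in an account of another trial's side effects and appears neither in the exclusion criteria nor in the dosing section, where the operative text is case-by-case dose modification. The firm rule, for glucose, has no rate. Because the stated aim concerns pharmacologic response, an on-treatment estimate is also a defensible target. All of this stands, and it is why the point is minor.

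Two further readings are tempting, and the documents do not support either. A reader might infer that the metformin effect will be overstated; the sign depends on k, which nothing in the plan fixes. A reader might also infer that the plan orders removed participants' data to be dropped; it does not say so. The loss follows in practice because outcomes are not collected after removal, and how much a single period contributes depends on a model choice left open.

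The safety committee's six-monthly review of drop-outs makes losses visible to it. It neither restores the outcomes nor defines the analysis set.

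A fix could also do harm. Having an unmasked physician decide who starts period 2, or delaying the diarrhea trigger until dose modification has failed, would add blinding and safety costs. The change proposed here does neither.

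**Conclusion.** The inconsistency is real and can be read directly from the text: two stated rules remove randomised participants for on-treatment events, the run-in that one of them names does not exist, and the primary analysis is called intent-to-treat. The numerical consequence is small and of unknown direction: about one or two participants if the cited 3-5% applies to metformin titration here, a shift of 0.06-0.15 SE if those removed would show no effect and the true effect is 2-3 SE, and probably few removals for low glucose. At least one diarrhea removal is more likely than not under that assumption (60-83%), so the protocol needs an answer in advance. Severity: minor.

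**What to change.** In the text after Table 3:

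1. Delete the word run-in.
2. Keep both safety triggers as they stand, but make them reasons to stop study drug, not to leave the study.
3. After glucose below 60 mg/dL, stop study drug permanently in both periods, so that no unmasked decision about period 2 is needed.
4. For diarrhea, handle stopping under the existing case-by-case rule in Interventions and Interactions, without unmasking to decide period 2.
5. Ask participants who stop to attend the scheduled Mid and FV visits, and analyse them in their randomised sequence.
6. Randomise any added participant afresh and count that person as an extra, not a substitute.
7. Report stops by sequence and period, and give an on-treatment estimate as secondary.

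The cost is a few sentences and no new visits. The primary estimate is slightly diluted, by about 3-5% if those stopped for diarrhea show no effect. A placebo-first participant who meets the glucose trigger in period 1 would never receive metformin yet would be analysed as randomised; the number is unknown but probably very small. The on-treatment estimate covers the pharmacologic-response aim. Participants who are off drug are asked to attend visits they might otherwise have skipped.

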## **Subject Recruitment Methods**

We will recruit these individuals using community-based recruitment strategies including newspaper ads and mass mailings. We will also advertise in the VITAL newsletter (BG99-559) and participate in community outreach events.

## **Informed Consent**

Written informed consent will be obtained from each subject. The informed consent process will follow

the procedures of the WFSM Institutional Review Board. The study interviewers will explain the purpose, methods and extent of the study to prospective participants. The potential participant is asked to read the informed consent form and ask questions. The form is written in simple easy to understand language. We require study staff to review all of the key aspects of the study verbally with the potential participants. Staff is provided with a structured checklist for this purpose. Staff is then required to question potential participants to ascertain whether s/he has understood the information. Potential participants who are illiterate or have impaired vision must have the consent read to them, followed by review of the checklist, opportunity for questions, and discussion. This process will take place in a quiet, private room. A copy of the signed and dated consent form will be given to participants, and the original document will be placed in subjects' individual study files, which will be stored in a secure location. In compliance with the Health Insurance Portability and Accountability Act (HIPAA) and the Standards for Privacy of Individually Identifiable Health Information of the Department of Health and Human Services, we will access personal health information only after obtaining informed consent.

### **Confidentiality and Privacy**

All data are obtained for research purposes only. Confidentiality of data is maintained by using research identification numbers which uniquely identify each individual. Data will be used only in aggregate and no identifying characteristics of individuals will be published or presented. The information collected has a low potential for abuse because the data do not address sensitive issues. Nevertheless, appropriate measures are taken to prevent unauthorized use of study information. Research records are kept in a locked room. Data access will be limited to study staff. Information linking IDs to individuals is kept on a secure, password-protected server to which only authorized study personnel will have access. Data and records will be kept locked and secured, with any computer data password protected. A web-based data entry system will be created for this study which will allow access only to study staff (user id and password required to access). Blinded staff will not have access to blinded study information on the web-based database. Computer files are stored on file servers, which are backed up each night and stored for easy retrieval in case of emergency. Files may not be obtained from the research unit by persons other than the research personnel, who are asked to sign a document agreeing to maintain the confidentiality of the information. No data files distributed for analysis will include personal information. No reference to any individual participant will appear in reports, presentations, or publications that may arise from the study. After the study is completed, the data will be stored with other completed research studies in a locked secure area.

